## **The Null Hypothesis**

There is no difference between SMART and ART in arresting caries, success, and retention rate as well as their impact on the oral health-related quality of life.

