## Aim of the Study

### Primary Aim

This study aims to evaluate and compare the clinical outcomes of **Silver-Modified Atraumatic Restorative Treatment (SMART)** and conventional **Atraumatic Restorative Treatment (ART)** in the management of carious primary molars in preschool children. This comparison includes:

- **Success rate:** which include restoration integrity, marginal adaptation, absence of secondary caries, and tooth vitality.
- **Retention rate:** Determined by monitoring whether the restoration remains fully or partially retained over time
- **Caries arrest:** where arrested lesions present with hard, darkened surfaces and no progression in lesion size

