## **Outcome Measurements:**

The primary outcome measure in this clinical study is the success of the ART restorations placed. The children will be examined 6 months after placement of ART restorations (Jiang et al., 2016).

The same instruments used in the baseline examination will be used in the follow-up examinations. The status of the restorations and restored teeth will be assessed and recorded using codes and criteria commonly adopted in previous clinical studies of ART restorations (Lo et al., 2007).

0 = restoration present, no caries, no marginal defects, or wear

1 = restoration present, no active caries, slight defects or wear not greater than 0.5 mm

2 = restoration present, marginal defects greater than 0.5 mm

3 = restoration present, wear greater than 0.5 mm

4 = restoration present, active caries found associated with the filling

5 = restoration missing, no active caries, surface hard to gentle probing

6 = restoration missing, active caries found, surface soft to probing allowing penetration of the tip of a blunt probe

7 = tooth with signs of pulpal pathology

8 = tooth missing, extracted due to caries

9 = tooth naturally exfoliate

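### Caries arrest is a compared outcome, but the follow-up codes do not record the features that define it, and no rule maps codes to arrest

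*Combined protocol and SAP*

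**What the plan says.** The Null Hypothesis names arrest first among the clinical outcomes: "There is no difference between SMART and ART in arresting caries, success, and retention rate". The Primary Aim lists success, retention and caries arrest, and describes arrest in these terms: "where arrested lesions present with hard, darkened surfaces and no progression in lesion size". It describes retention as "Determined by monitoring whether the restoration remains fully or partially retained over time".

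Outcome Measurements makes success of the restorations the primary outcome, sets the examination at 6 months, and gives one list of codes, 0 to 9, for restorations and restored teeth. Surface hardness appears in two of them: "5 = restoration missing, no active caries, surface hard to gentle probing" and "6 = restoration missing, active caries found, surface soft to probing allowing penetration of the tip of a blunt probe". With the filling in place, codes 0 and 1 report no caries or no active caries, and active caries has its own code: "4 = restoration present, active caries found associated with the filling". Two further filling-present codes describe only the restoration: "2 = restoration present, marginal defects greater than 0.5 mm" and "3 = restoration present, wear greater than 0.5 mm".

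Under Methods, both groups have the cavity filled with glass ionomer, and radiographs are mentioned only at baseline and only as needed. Statistical Analysis compares outcomes between the techniques with Fisher's exact test. It does not name arrest as a variable.

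**The concern.** The definition of arrest and the scale meant to measure it do not fit each other. The definition rests on what can be seen and felt on the lesion surface and on whether the lesion has grown. Both treatments cover that surface, and the codes describe mainly the restoration.

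Without a stated rule, someone must decide later which codes count as arrested, possibly with the results in view. Different reasonable rules could give different answers, most obviously for teeth coded 2 or 3. If arrest were instead read directly from the surface, only teeth that had lost the filling could contribute. That group forms after randomisation and is selected by retention, which is itself a compared outcome.

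**Working it through.** The plan gives no figure for this outcome, so the check matches each code under Outcome Measurements to the three features in the Primary Aim.

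| Code | Filling | Hardness | Colour | Lesion size | Caries status |
|---|---|---|---|---|---|
| 0 | present | no | no | no | no caries |
| 1 | present | no | no | no | not active |
| 2 | present | no | no | no | not stated |
| 3 | present | no | no | no | not stated |
| 4 | present | no | no | no | active |
| 5 | missing | hard | no | no | not active |
| 6 | missing | soft | no | no | active |
| 7 | not stated | no | no | no | not stated (pulpal pathology) |
| 8 | tooth extracted | no | no | no | caries given as the reason |
| 9 | tooth exfoliated | no | no | no | not stated |

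Counts from the table:

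- Hardness: 2 of 10 codes (5 and 6), both with the filling missing; 0 of the 5 filling-present codes.
- Colour: 0 of 10. Lesion size: 0 of 10.
- All three features together: 0 of 10, so no code can confirm arrest as defined.
- Code 6 contradicts arrest directly, through a soft surface. Code 4 contradicts it through active caries, without a hardness reading.
- Caries status among the filling-present codes: 3 of 5 (0, 1 and 4).

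Other possible sources were then checked.

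- *Partial loss.* The Primary Aim recognises partly retained fillings, which might expose some of the surface. No code records partial loss or a surface finding in that state.
- *Repeat of the baseline instruments.* Outcome Measurements says these are reused at follow-up, but not that ICDAS is scored again or that the lesion is measured. By the Introduction's own account, ICDAS works from what is visible on the surface, so it would not reach beneath an intact filling.
- *Radiographs.* None is scheduled at follow-up, and baseline films are not taken for every tooth, so growth of the lesion cannot be followed this way.

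For scale only: if the 64 or 80 molars in the sample-size section are totals over both arms, each arm has 64/2 = 32 or 80/2 = 40 teeth. One tooth coded 2 or 3 then carries 1/32 = 3.1 or 1/40 = 2.5 percentage points of its arm. The documents do not say how often these codes will occur, so this is not a bias estimate.

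**The case against.** The strongest reply is that the Primary Aim describes how arrested lesions look in the clinic, while Outcome Measurements is where measurement is specified. On that reading the data exist: codes 0, 1 and 5 against codes 4 and 6 separate inactive from active caries, and all that is missing is a sentence of mapping. Much of this stands. It would be wrong to infer that the trial records nothing about caries, since five codes state its activity. But the mapping is nowhere given, the proxy is not the outcome as defined, and codes 2 and 3 remain unassigned.

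A second reply is that the code list is adopted from earlier ART studies, whose criteria may already rank active caries above marginal defects and wear. That is possible, and the documents do not exclude it. The protocol does not state such a rule, however, so a reader cannot rely on it.

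A reader might also infer that arrest will be analysed only in pairs where both fillings were lost, leaving too few pairs to test. The documents do not support this. No such analysis is planned, and no 6-month loss rate is given from which to count pairs.

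Finally, a proxy built from these codes overlaps with freedom from secondary caries, which the Primary Aim already counts within success. That is a real limitation and should be stated with the endpoint.

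**Conclusion.** The point holds in this form: arrest as the Primary Aim defines it cannot be derived from the codes the plan will record, and the proxy the codes do support has no stated mapping. The size is a count: 0 of 10 codes record colour or lesion size, 2 of 10 record hardness (only with the filling missing), and 2 of the 5 filling-present codes leave caries status open.

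This rests on the code list being the only clinical record at follow-up, as the text indicates, and on an intact filling hiding the lesion surface in both arms.

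A reader might go further and conclude that the trial's primary result is compromised. The documents do not support that: success is named separately as the primary outcome, its definition is not affected by this point, and no bias size is claimed. Nor do they establish that the arrest rule was chosen after seeing data. Statistical Analysis is written in the past tense but Outcome Measurements in the future, so the timing is unclear. The change should be made, but the point does not invalidate the trial.

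**What to change.** In the Null Hypothesis and Primary Aim, replace caries arrest with *no active caries at the restored tooth*, secondary to success. Describe it as a proxy that cannot see beneath a retained filling and that overlaps with the secondary-caries component of success. Under Outcome Measurements, state how each code counts:

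- Codes 0, 1 and 5: no active caries.
- Codes 4 and 6: active caries.
- Codes 2 and 3: no active caries, provided the protocol states before the examinations that code 4 takes precedence when active caries is found. Alternatively, record caries activity as a separate yes/no item and classify these teeth from it.
- Code 8: failure.
- Code 7: report both ways, once as failure and once left out, because the code list does not attribute pulpal pathology to caries. Counting it as failure brings the endpoint closer to success, and the report should say so.
- Code 9: not evaluable; report how many pairs this removes.

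The groups cover all ten codes: 3 + 2 + 2 + 1 + 1 + 1 = 10.

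In Statistical Analysis, compare the arms on this endpoint with a paired method such as exact McNemar instead of Fisher's exact test, which ignores the matching of teeth within a child.

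If the examinations are already done, a precedence rule cannot be applied to single recorded codes. Count codes 2 and 3 both ways and label the endpoint post hoc.

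The cost is wording in four sections and at most one yes/no item per tooth at 6 months; if the examinations are complete, no new data are needed. What is given up is a claim about arrest itself.

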Caries may have a negative impact on oral health-related quality of life in preschool children. Oral health-related quality of life (OHRQoL) is a multidimensional concept that consists of subjective evaluations of oral health, functional and emotional well-being, satisfaction with care, and sense of self (Ruff et al., 2022).

International Caries Detection and Assessment System (ICDAS) employs an evidence-based and preventively oriented approach, it is a detection and assessment system classifying stages of the caries process by using visual surface characteristics to measure surface changes and potential histologic depths of caries lesions. The classification criteria, and associated estimates of caries activity, are based on the histological extension of lesions into tooth structure. The scores are on a 7-point rating scale (Young et al., 2015).

Minimal intervention dentistry (MID) is a philosophy of dental care that aims to keep teeth healthy and functional throughout a person's life. It recommends preserving not only sound tooth tissues but also tissues with the potential to remineralize so as to maximize the healing potential of the tooth (Jiang et al., 2021).

Atraumatic restorative treatment (ART) is a minimally invasive approach for the management of cavitated lesions. The ART procedure involves removal of soft carious dental tissues using hand instruments without giving local anesthesia and placement of restoration using adhesive dental material, mostly high viscosity glass ionomer cement (GIC) which provides chemical adhesion to the tooth surface, fluoride release, and biocompatibility (Jiang et al., 2021).

Glass Ionomer Cement used in ART is considered as a satisfactory option for treatment of decayed primary teeth in young ages and a source of fluoride release which may help in arresting caries and preventing the development of new ones and it's acceptable from the child and parents due to its white color (Duangth et al., 2017).

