## **Materials and Methods**

### **Study design:**

Randomized clinical trial using split-mouth design technique.

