#### **• Grouping**

- **Group A** the teeth will be restored by ART using high viscosity glass ionomer cement (GC Fuji IX )
- **Group B** the teeth will be treated with silver diamine fluoride 38%, and then restored by high viscosity Glass Ionomer cement (Fuji IX), both according to manufacturer instructions.

- **Inclusion Criteria:**

- Generally healthy children of ages 3 to 6 years old, who have at least 2 bilateral decayed primary molars with occluso-proximal carious dentin lesions (scores 4 or 5) according to the International Caries Detection and Assessment System (ICDAS II)
- Children with negative (Rating 2) and positive (Rating 3) behavior, according to Frankel's behavior rating scale

- **Exclusion Criteria:**

- Children with systemic diseases/conditions
- Children with definitely positive and negative behavior
- Teeth with signs of pulpal pathology (abscess, fistula, mobility)
- Teeth with very deep cavities
- Teeth with signs of irreversible pulpitis

- **Ethical Approval:**

Written informed consent should be signed by patients' parents before participation in the study.

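### The caries-arrest definition requires a darkened surface, which the silver agent given only in the SMART arm may itself produce, so the arrest comparison is exposed to bias toward SMART

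*Combined protocol and SAP*

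**What the plan says.** The Primary Aim section compares SMART and ART on three items: success, retention and caries arrest. Arrest is the item "where arrested lesions present with hard, darkened surfaces and no progression in lesion size". The Null Hypothesis section also names arrest.

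Under Grouping, Group A is the arm in which "the teeth will be restored by ART using high viscosity glass ionomer cement (GC Fuji IX". Group B is the arm in which "the teeth will be treated with silver diamine fluoride 38%, and then restored by high viscosity Glass Ionomer cement (Fuji IX". The silver agent is the added component in Group B, and both arms receive the same glass ionomer. The Introduction says of glass ionomer that "it's acceptable from the child and parents due to its white color". The design is described as "Randomized clinical trial using split-mouth design technique".

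Outcome Measurements names success of the restorations as the primary outcome measure. It is assessed at 6 months on codes 0 to 9, two of which read "1 = restoration present, no active caries, slight defects or wear not greater than 0.5 mm" and "4 = restoration present, active caries found associated with the filling". No code mentions colour. Codes 5 and 6, which apply when the restoration has been lost, separate inactive from active caries by hardness on probing. The Primary Aim section describes success as an outcome "which include restoration integrity, marginal adaptation, absence of secondary caries, and tooth vitality". The plan does not say which codes count as success. It describes no masking of the examiner and gives no instruction on how to treat colour.

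**The concern.** Arrest is judged partly on a sign that one of the two treatments may cause directly. If so, the sign no longer reflects only the state of the lesion; it also reflects the arm. Two lesions in the same true state, both hard and not progressing, could be classified differently: arrested in SMART because the agent darkened the surface, not arrested in ART because nothing did. A difference in arrest could then appear with no difference in caries control. It would bear on a comparison named in both the aim and the null hypothesis.

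A second, weaker question is whether colour can reach the primary outcome. Absence of secondary caries is part of success, and the plan does not say how activity is recognised when the restoration is still in place.

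**Working it through.** The plan states no figure on this point, so there is none to reproduce. The check has three steps.

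**1. Apply the arrest definition as written.** All three conditions must be met: hard, darkened, no progression.

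| Lesion at 6 months | Hard | No progression | Dark | Arrested under the plan | Arrested if colour is dropped |
|---|---|---|---|---|---|
| SMART, dark from the agent | yes | yes | yes | yes | yes |
| ART, dark | yes | yes | yes | yes | yes |
| ART, not dark | yes | yes | no | **no** | **yes** |
| SMART, dark from the agent | no | yes | yes | no | no |

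The colour condition changes only the third row. The definition does not pass a soft SMART lesion as arrested. It can fail a hard, non-progressing ART lesion.

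**2. Size for the arrest comparison.** All inputs here are assumptions. Let a be the proportion of lesions that are hard and non-progressing, equal in both arms. Let d be the fraction of those in ART that are not dark, and s the same fraction in SMART.

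- Observed arrest: SMART a(1 − s), ART a(1 − d).
- Spurious difference: a(d − s). It favours SMART whenever s < d.

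Take s = 0, meaning the agent darkens every such SMART lesion. Take 40 teeth per arm, which is the planned 80 molars split equally with no loss (80/2 = 40). The Statistical Analysis section uses Fisher's exact test between arms at one time point. The table gives the probability that a two-sided Fisher test reaches p ≤ 0.05, with arms treated as independent as that test does.

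| a (both arms) | d = 0 | d = 25% | d = 50% |
|---|---|---|---|
| 10% | 1.7% | 2.1% | 4.3% |
| 20% | 2.8% | 5.5% | 16.2% |
| 30% | 2.8% | 7.8% | 28.1% |
| 50% | 3.3% | 15.4% | about 56% |

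At a = 50% the spurious difference is 50% × 25% = 12.5 points (50% versus 37.5%), or 50% × 50% = 25 points (50% versus 25%). At a = 10% it is 2.5 or 5 points. With 32 per arm (64/2) and a = 50%, the three probabilities are 3.3%, 12.7% and 46.0%. For d > 0, nearly all rejections favour SMART. For context only, the Introduction cites arrest rates of 31% to 79% after one application of 38% silver diamine fluoride. Those are not rates for the restored teeth in this trial.

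**3. Can colour reach the primary outcome?**

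- Codes 5 and 6: activity is fixed by probing. Colour has no role.
- Codes 2 and 3: these record marginal defect or wear and carry no statement about caries.
- Codes 0, 1 and 4: these require a call of no caries, no active caries or active caries beside a restoration that is present, and give no criterion for it. This is the only opening.

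If an examiner took dark margins as inactive, true activity of 15% in both arms with one third of active SMART margins missed would be recorded as 15% × (1 − 1/3) = 10% against 15%. That is 5 points in favour of SMART. If dark margins were instead read as secondary caries, the error would run against SMART. Nothing in the documents selects between these or excludes zero.

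**The case against.** The strongest reply has five parts.

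- **Colour is only one of three joint signs.** A soft, dark lesion is not arrested under the plan. This is correct, and it rules out the reading that darkening alone earns an arrest. It does not protect an ART lesion that is hard and stable but not dark.
- **The primary outcome does not use colour.** This stands. A reader might infer that the plan tilts the primary outcome toward SMART. The documents do not support that. The darkening wording belongs to the arrest item, and no text carries it into the codes. Code 5, in the same list, already describes inactive tissue by hardness, so it is the nearer guide for code 4. Any effect on success also depends on a cut-off that is not stated: if code 2 counts as failure, moving a tooth from code 4 to code 2 changes nothing.
- **Most treated dentine is covered.** With the restoration in place, colour may show only at margins or defects. This stands and limits how many teeth are exposed, for arrest as well as for success.
- **The documents do not say that silver darkens dentine.** This is correct. The Introduction describes the agent's action without mentioning staining. The point therefore rests on a declared assumption. A reader might also infer that the examiner will certainly recognise the arm, helped by the contrast within one mouth. That is possible under the assumption but is not established.
- **The cited code set may define activity.** It may, but the plan does not reproduce such a definition, so an examiner working from the plan has none for codes 0, 1 and 4.

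**Conclusion.** The concern holds for the caries-arrest comparison. As written, the definition contains a condition that SMART can meet by treatment alone and that can exclude an equally hard and stable ART lesion. The bias runs toward SMART as long as fewer hard, non-progressing lesions lack a dark surface in SMART than in ART. It rests on the assumption that the silver agent darkens dentine and on lesion surfaces being visible at 6 months.

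Its size is unknown. In the illustrations it runs from trivial (10% true arrest, a quarter of those ART lesions not dark: 2.5 points, 2.1% rejection) to serious (50% and one half: 25 points, about 56% rejection).

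For restoration success the documents show only a gap: activity beside a retained restoration has no criterion. Neither the size nor the direction of any resulting error can be derived. The change is worth making because it is cheap and takes a treatment-caused sign out of an outcome. The finding does not undermine the design as a whole.

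**What to change.** - In the Primary Aim section, delete the word *darkened* and define arrest by hardness and no progression in size.
- In Outcome Measurements, judge caries activity in codes 0, 1 and 4 by softness on gentle probing with the blunt probe, as codes 5 and 6 already do, and state that colour is disregarded.
- State which codes count as success, so that the effect of a code 4 call is known.
- Where existing staff allow, have the 6-month examiner score without the allocation list or treatment notes. Report that masking may be incomplete.

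The cost is mainly wording: no extra visit, instrument or teeth. The downside is a slight departure from the cited code set, which should be noted when results are compared with studies that used it. The Statistical Analysis section is written in the past tense, so examinations may already be complete. In that case, re-derive arrest without colour if hardness and progression were recorded separately. Otherwise, report the colour condition as a limitation of the arrest comparison.

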### Secondary Aim

- To describe the change in oral health-related quality of life of preschool children before and after placement of ART and SMART restorations.

## **Materials and Methods**

### **Study design:**

Randomized clinical trial using split-mouth design technique.

### **Study setting:**

Inpatients at the clinics of Beirut Arab University.

### **Study Sampling:**

#### **• Size formula**

The sample size was specified by using the G power test, assuming a statistical level of significance of 5% and power 80% with normal distribution, and 0.367 effect size calculated from means and standard deviation of 2 groups obtained from a previous study (Jiang et al., 2021). The original sample size will be 64 molars, and will be increased up to 80 with a possible dropout.

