## **Statistical Analysis:**

Data analysis was carried out by using the statistical software SPSS (version 28, IBM SPSS statistics, USA. Based on the results of the Shapiro-Wilk test, most of the data were determined to follow a normal distribution. The significance level was set at  $p \leq 0.05$ . The qualitative data were presented as frequencies and percentages, whereas the quantitative data were presented as median, range, mean, and standard deviation values. Paired Samples

t-Test was used to compare the means of two related groups, it was used to assess changes in ECOHIS scores at baseline and after intervention. Fishers exact test was used to compare the outcomes between ART and SMART at a single time point. Categorical data like the relation between the success rate of both treatments and the type of the cavity was analyzed by using the Chi-Square Test of Independence. The significance level was set at  $p \leq 0.05$ .

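### The 80% power stated for 64 molars is not a power for the primary comparison, which is paired and categorical

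*Combined protocol and SAP*

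**What the plan says.** - **Size.** The Size formula section names only the software, 5% significance, 80% power, a normal distribution and a "0.367 effect size calculated from means and standard deviation of 2 groups obtained from a previous study". It then states: "The original sample size will be 64 molars, and will be increased up to 80 with a possible dropout". It gives no effect-size metric, test, sidedness, outcome or within-pair correlation.
- **Design.** Study design reads "Randomized clinical trial using split-mouth design technique".
- **Primary outcome.** Outcome Measurements says "The primary outcome measure in this clinical study is the success of the ART restorations placed", assessed at 6 months on codes 0 to 9. One of these is "5 = restoration missing, no active caries, surface hard to gentle probing". The Primary Aim describes success through components "which include restoration integrity, marginal adaptation, absence of secondary caries, and tooth vitality", but nothing links those components to the codes.
- **Test.** Statistical Analysis says "Fishers exact test was used to compare the outcomes between ART and SMART at a single time point". The only paired test named is a t-test for change in the quality-of-life score over time.
- **Tense.** The same section is written as though the work were done: "Data analysis was carried out by using the statistical software SPSS".

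**The concern.** The Size formula section is the only justification of the trial's size. It rests on a difference in means, whereas the primary result will be a comparison of success proportions between teeth in the same mouth. The analysis then uses a test for independent groups. Power depends on the outcome, the test and the correlation within pairs, and the sizing statement addresses none of these for the primary comparison.

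The null hypothesis is one of no difference between the techniques. A non-significant result would therefore tend to be read as evidence of equivalence from a trial with 80% power, when that power has not been shown.

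**Working it through.** **Inputs from the plan:** two-sided tests at alpha 0.05 (sidedness is my assumption), target power 80%, effect size 0.367, 64 molars. Assumed: equal allocation, so 32 molars per technique or, in a split-mouth layout, at most 32 pairs.

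**1. Can 64 be reproduced?** The inputs do not fix a formula, so several readings were tried.

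| Reading of 0.367 | Needed for 80% | Power at 64 molars |
|---|---|---|
| Cohen's d, two independent groups, t-test | 118 per group | 30% |
| Paired dz, t-test | 61 pairs (122 molars) | 52% (32 pairs) |
| Paired dz, Wilcoxon signed-rank | 64 **pairs** (128 molars) | 50% (32 pairs) |
| Cohen's f, so d = 2 × 0.367 = 0.734, independent groups, t-test | 31 per group (62 molars) | 82% |
| Cohen's f, independent groups, Mann-Whitney | 32 per group (64 molars) | 80.6% |

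The rank tests use an asymptotic relative efficiency of 3/π. The signed-rank reading has 80.6% power at 64 pairs. So 64 fits a calculation on unpaired teeth, and it also fits a paired calculation whose unit would be pairs. The dropout step is consistent with an unstated 20% rate: 64/(1 − 0.20) = 80.

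**2. If 0.367 is a standardised mean difference and there are 32 pairs.** As a paired difference, the noncentrality is 0.367 × √32 = 2.08 on 31 degrees of freedom, which gives 52% power (62% if all 40 pairs are evaluable). As a between-tooth difference, dz = 0.367/√(2(1 − ρ)):

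| ρ | 0 | 0.3 | 0.5 | 0.7 |
|---|---|---|---|---|
| dz | 0.260 | 0.310 | 0.367 | 0.474 |
| Power | 30% | 40% | 52% | 74% |

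A correlation of about 0.74 is needed to reach 80%.

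**3. The primary outcome.** The plan gives no success rates, so those below are **assumptions for illustration**. With success probabilities p1 and p2, the chance that both teeth succeed is p1·p2 + ρ√(p1(1 − p1)p2(1 − p2)). For 60% v 85% at ρ = 0.3 this is 0.510 + 0.3 × 0.175 = 0.562, leaving discordant probabilities of 0.038 and 0.288. Full enumeration for 32 pairs gives:

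| Assumed rates | Fisher, ρ = 0 / 0.3 | Exact McNemar, ρ = 0 / 0.3 |
|---|---|---|
| 60% v 85% | 53 / 53% | 50 / 66% |
| 70% v 90% | 41 / 39% | 39 / 51% |

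The mirror rates 15% v 40% and 10% v 30% give the same powers. This matters because the only Class II success rate in the Introduction is about 15%, though at 24 months and not 6.

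**4. What Fisher's test does to the error rate.** With both true rates at 70% (assumed) and 32 pairs, it rejects 2.8 / 0.9 / 0.2% of the time at ρ = 0 / 0.3 / 0.5. Exact McNemar rejects 2.6 / 2.1 / 1.5%.

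**5. Precision.** The half-width of the 95% interval for the paired difference is 1.96√((p10 + p01 − (p10 − p01)²)/32), where p10 and p01 are the two discordant probabilities. With both rates at 60% and ρ = 0, it is 1.96√(0.48/32) = 24.0 points. With both at 85% and ρ = 0.3, it is 1.96√(0.1785/32) = 14.6 points.

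**The case against.** The strongest reply is that the sizing is merely brief. Cohen's f on two groups reproduces 64 closely, so nothing is wrong with the arithmetic. That stands: a reader might infer from the 118-per-group or 61-pair figures that 64 is a mistake, but the documents do not support this because the metric is not stated. The reply does not rescue the power claim, since the readings that give 64 molars treat teeth as unpaired and the outcome as continuous or ranked.

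Three other inferences go too far.

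- *Fisher's test on paired teeth inflates false positives.* With positive correlation it becomes conservative. The harm is lost power.
- *The trial has about 40% or 50% power for success.* Those figures rest wholly on assumed rates and correlations. The documents support only the statement that this power cannot be derived.
- *Success is undefined.* The Primary Aim's list already points to code 2 (large marginal defects) and code 5 (restoration missing) as failures, and probably code 3 (wear over 0.5 mm). Codes 1 and 9 are the ones mainly open. An explicit cut-off is still needed.

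It is also fair to say that, if the data are already in hand, a new power table cannot change the trial. That affects which part of the remedy matters most.

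**Conclusion.** The point holds in this form: the stated 80% power is not a power for the trial's paired, categorical primary comparison, and the planned test does not use the pairing. Across two-sided readings of 0.367 on means, power at 64 molars runs from 30% to 82%. The upper end is reached only by leaving out the split-mouth structure. Whether 64 was meant as molars or pairs cannot be settled from the documents; the signed-rank match is a reason to check, not proof of an error.

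The conclusion that the sizing and the analysis do not match needs no assumed rate. The size of the loss from Fisher's test does: about 12 to 13 points at a correlation of 0.3 under the rates used here. The plan should be corrected, but the trial is not invalidated.

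**What to change.** Enrolment stays as planned.

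1. **Sizing.** Check the source calculation, including whether 64 meant molars or pairs. Withdraw the 80% claim, or restate it for the paired binary outcome with metric, test, sidedness, assumed success rates and within-pair correlation. If 64 molars stands, describe it as at most 32 pairs (40 with the dropout allowance) and give the number of children.
2. **Analysis.** Replace Fisher's test for ART v SMART with a paired method: McNemar, or one that allows for clustering if a child contributes more than one pair. Report the paired difference in success with its 95% confidence interval, and do not read a non-significant result as no difference.
3. **Endpoint.** State which of codes 0 to 9 count as success, settling codes 1 and 9 in particular.
4. **Timing.** The analysis section is in the past tense. If outcome data have been seen, label the paired test and the success definition as set after the data. The interval then matters more than a new power table.

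**Cost:** a reworded sizing paragraph, one changed analysis sentence and one new sentence defining success. The stated power becomes less favourable and depends on assumptions. In the illustrations, exact McNemar loses 2 to 3 points of power against Fisher's test if the within-pair correlation is near zero.
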